# 4.2 Aim 1 Methods: Conduct a geographic scan of liver disease rates and determinants of disparity

**A. Study Population.** As part of IRB 17-9031, we will use **Registry data from the Pennsylvania (PA) State Liver Cancer Registry.** This data has about 18,000 incident liver cancer cases (primarily Hepatocellular Carcinoma cases) diagnosed from 2003-2015 from the cancer registry. For each patient in the registry, we will geocode or request existing geocodes at the census tract level to represent the neighborhood in which they live. We will exclude cases missing geocodes, address information or with P.O. Box addresses.

**B. Area-level Determinants of Disparity.** As part of IRB 17-9031, area level determinants of disparity were selected from Year 2010 U.S. Census and the 2010-2015 American Community Survey. In this analysis, we focus primarily on race/ethnic breakdown by neighborhood (i.e. % non-Hispanic Black; %Hispanic). We also collected information on the estimated total population of each census tract, gender breakdowns and reported age ranges within each census tract to allow for stratification/adjustment. Area-level determinants of Disparity from the U.S. Census data were linked at the census tract level to the PA State Cancer Registry.

C. Database Linkage and Geocodes. Geocoding of liver cancer data was completed a part of IRB 17-9031. Geocoding is the process of assigning latitude and longitude to a point, based on street addresses, city, state and ZIP code. Geocodes are defined here in terms of Federal Information Processing Standard (FIPS codes) and will link each case to the geographic area in which they live. These codes include unique identifiers for each state (two digits), each county (3 digits), and each census tract (6-digits) in the U.S. On average, there are approximately 4,000 residents located in a single census tract; as such, census codes can serve as unique identifiers for census tract-level neighborhood characteristics[13], and household information is not easily identifiable[13]. Patient addresses, including street address, city, state, and ZIP code, are needed to create geocodes and assign individual patients to a census tract. The Pennsylvania Cancer Registry and Pennsylvania Department of Health have provided patient As part of IRB 17-9031, we implemented additional protections for our address for geocoding. geocoded study populations by employing a "false coordinate system" to decouple household addresses from individual personal data attributes. That is, we have mapped the data in such a way that the true geographic location is not stored in the GIS software. For instance, the actual position of an address might be described by the coordinates: -125.652, 24.229. The statistical tools within GIS enable us to very simply alter the true coordinate values by adding or subtracting a fixed value to all the X and Y geographic coordinates in the dataset. We intend to employ a "minimum-maximum false coordinate range" of values 1-8 — to ensure that the confidentiality of the study participants' household addresses are, not in any way, compromised. Further, for areas or census tracts with a minimal number of patients (i.e. <6 patients), we employed geographic aggregation techniques and small area estimations to further protect confidentiality[14]. Once geocodes were created from PA Cancer Registry data, patient address information were removed and destroyed, as only geocoded, de-identified data was kept and used for analysis.

**D. Liver Disease Definitions.** Incidence rates of hepatocellular cancer(HCC) and early (Stage 1/2) versus late stage (Stage 3/4) HCC.

# 4.3 Aim 2 Methods: Identification of Community Partners and Development of Education Session

**A. Identification of Community Partners**. Working with long-standing community partners, the Office of Community Outreach (OCO) will isolate those located within the "high-risk" communities identified via geo-spatial analysis. Community sites may include community-based, faith-based, academic, primary care community practices or non-government organizations. Once we have worked with a set of identified partner sites, we will seek to establish additional partnership to expand our reach.

Historically, OCO networks with community partners to offer our education sessions via our community speaker's bureau. The sessions are generally one-hour long and are offered at no cost. For the purposes of this study, we will inform the partner sites that this education session is part of a pilot research project we are conducting to determine the community's understanding of the liver cancer burden in the region and to assess their interest in community health. Based on this conversation, the partner will inform us of their interest in participating.

**B. Education Session.** The intervention consists of a PowerPoint presentation (See Appendix B), an educational brochure, and a pre/post test (Appendix C). An OCO trained health educator will provide delivery of the session; didactic and interactive modalities will be employed to engage participants. This includes sharing liver cancer anatomical models and encouraging participants to ask questions during the Q/A period.

The module will provide participants with a general overview of cancer and will then provide liver cancer specific information. Included in the module is risk factors, symptoms, screening, and diagnosis and treatment information. The PowerPoint presentation will be accompanied by an educational brochure for participants to take home with them. Following the liver cancer information, the health educator will provide an overview of neighborhood health and what this project aspires to yield from our approach.

The PowerPoint liver module is written at a 7.3 grade level and has been vetted for accuracy by clinician [name] at Fox Chase Cancer Center. Behavioral Scientists, [name]., [name]. and OCO Sr. Director [name] have developed the pre/post tests. The final versions has been reviewed by the director of health communications, [name] for plain language review. Once approved by IRB, OCO will proceed with translation of the documents into Spanish, using the TUHS approved vendor(s).

Because in-person education sessions cannot be held during the COVID-19 pandemic, the educational slides will be converted to a set of handouts that will be sent to the participant (along with the educational brochure). The educational intervention materials will be sent via US mail to participants who do not have reliable internet access, and those who prefer to view the materials online will be offered the choice of having them emailed or texted, or viewing them on Zoom. The health educator will call the participant to review the educational materials over the telephone (or Zoom). By default, the intervention will be conducted over the telephone and only participants who indicate that they are comfortable utilizing a web platform will be offered the intervention over Zoom (or a similar program). Zoom instructions will be given over the telephone at the time of the intervention to those who opt to receive the intervention online. For analysis purposes, intervention delivery method (pre-COVID in-person/telephone/online) will be tracked, as well as the timing of the intervention relative to consent and baseline (immediate administration, i.e., after materials are mailed to the participant after consent and baseline).

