#### **B. Study Survey**

Once eligibility has been confirmed, informed consent has been obtained, participants will fill out a sign-in sheet that includes their street address. If the participant agrees to be contacted about this or future research after their participation, they will also be asked to write their telephone number on this form. Because the sign-in sheet contains identifiable information, it will be kept separate from survey data and will be linked by a study ID assigned to the participant after consent. The street address data will be geocoded for neighborhood analysis. Telephone numbers will be stored in a secure database. Once geocodes are created from the street addresses, hard copies of the sign-in sheets will be destroyed. After the sign-in sheet is collected, the study survey will be administered. Once approved, the English survey will be translated into Spanish language. Once translated, a modification will be submitted.

The study "pre" survey will be administered post informed consent process and prior to the educational intervention by OCO health educators (field staff). Upon completion of the educational module, a posttest survey will be administered. All survey data will be entered in the RedCap database.

Both the pre- and post-survey will contain measures of knowledge about liver risks and prevention, self-efficacy about talking to medical professionals about neighborhood risk, as well as demographic items (e.g. gender, race/ethnicity). The post survey will include similar knowledge questions as well as additional questions specifically related to neighborhood health, including a program evaluation, outcome expectancies about learning about neighborhood health (i.e., the extent to which leaning about neighborhood health will be beneficial), and intentions to talk with clinicians about liver cancer, neighborhood health and liver cancer screening. **Primary outcomes** include pre-post changes in knowledge about liver cancer, interest in learning about neighborhood health, outcome expectancies for learning about neighborhood health, and participant intentions for talking to their doctors about liver cancer risk.

During COVID-19 closures, the survey will be administered over the telephone. Mailing and street address will be collected during recruitment, so that informed consent copies and intervention materials can be mailed to the participant.

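### The last listed part of the session states the project's hopes for its neighborhood approach, and the post-test follows, so any agreement this prompts cannot be separated from an education effect on two primary outcomes

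*Combined protocol and SAP*

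**What the plan says.** Section 4.3 B (Education Session) describes general cancer content, then liver cancer content, and then a closing part in which "the health educator will provide an overview of neighborhood health and what this project aspires to yield from our approach". No later component is listed. A question period is mentioned, but its position is not given.

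Section 4.4 B (Study Survey) sets the timing: "Upon completion of the educational module, a posttest survey will be administered". No delay is stated. On content it says: "The post survey will include similar knowledge questions as well as additional questions specifically related to neighborhood health". These include "outcome expectancies about learning about neighborhood health (i.e., the extent to which leaning about neighborhood health will be beneficial". The primary outcomes "include pre-post changes in knowledge about liver cancer, interest in learning about neighborhood health, outcome expectancies for learning about neighborhood health", together with intentions to talk to a doctor about liver cancer risk. Two of the four therefore concern neighborhood health.

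The pre-survey is given "prior to the educational intervention by OCO health educators (field staff", and an educator from the same office delivers the session. The text does not say who gives the post-test. It adds: "During COVID-19 closures, the survey will be administered over the telephone".

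Section 4.4 C plans no active follow-up. Section 14.2 compares pre with post by t-test or Wilcoxon test, and no control group is described.

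**The concern.** Teaching about neighborhood health is part of the intervention, and some change in interest and expectancies is intended. A statement of what the project hopes to gain is different in kind: it tells participants what the team would like to see, shortly before they rate how worthwhile the topic is. If some of them answer more favorably out of courtesy or agreement, that lift enters the pre-post change.

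A baseline would not remove it, because the statement falls between the two surveys. A control group, a delayed post-test, an independent survey administrator or a social-desirability check might help separate the two sources of change, but none is described. The fidelity checklist in section 17.0 checks that material is covered consistently and completely, so it would not detect the problem. The likely direction is upward, towards a positive finding on these two outcomes.

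**Working it through.** **1. Order of events.** Set side by side, the sections give: consent, pre-survey (4.4 B), liver cancer content, neighborhood overview with the project's aspirations (4.3 B), post-test on completion (4.4 B). During closures the slides become handouts. The timing that 4.3 B describes has materials mailed after consent and baseline and then reviewed by telephone or Zoom. If the handout carries the aspirations, a participant may read them before the call, but still between the two surveys.

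**2. Outcomes exposed.**
- Interest in, and outcome expectancies for, learning about neighborhood health: directly exposed.
- Knowledge about liver cancer: little affected, since agreement with the project's hopes does not supply correct answers.
- Intention to talk to a doctor: the primary item concerns liver cancer risk, so the link is weaker.

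**3. The plan's own figure.** Section 14.3 gives 50 to 100 participants, 80% power, 5% two-sided, and a standardized effect of 0.3-0.4 SD of the change. For paired data, n = ((1.960 + 0.842)/d)².
- d = 0.4: (2.802/0.4)² ≈ 49.1, so 50. The exact t calculation needs 52, and n=50 gives 79.2% power.
- d = 0.3: (2.802/0.3)² ≈ 87.2, so 88. The exact t calculation needs 90, and n=100 gives 84.4% power.

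The stated range reproduces, and this point disputes no figure in the plan.

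**4. Illustration of an agreement shift.** The documents give no size for such a shift, so b below is an assumption. Take zero true effect and a mean shift of b SD of the change score. The two-sided 5% paired t-test then follows a noncentral t with n − 1 degrees of freedom and noncentrality b√n. For b = 0.2 this is 0.2 × √50 = 1.41 at n=50 and 0.2 × √100 = 2.0 at n=100.

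| Assumed b | Rejects at n=50 | Rejects at n=100 |
|---|---|---|
| 0.1 | 10.7% | 16.8% |
| 0.2 | 28.4% | 50.8% |
| 0.3 | 54.8% | 84.4% |
| 0.4 | 79.2% | 97.7% |

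A shift of 0.2 is 0.2/0.4 = half to 0.2/0.3 = two-thirds of the planned effect. A larger sample raises the rejection rate, so more recruitment does not help. The table holds for any shift of that size. It shows how sensitive the test is and is no evidence about this particular statement.

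**5. Limit of the illustration.** It needs a baseline for the same items. Section 4.4 B calls the neighborhood questions additional on the post survey, while defining the outcomes as pre-post changes. Section 14.2 names knowledge, self-efficacy and intention, but not interest or expectancies. Whether these two outcomes will be tested in pairs is therefore unclear. A post-only rating would be more exposed to the same cue.

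**The case against.** The strongest reply has five parts.

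- **A reader might infer that the session tells participants which answer is wanted.** The documents do not say so. The aspirations stated elsewhere in the protocol concern insight into disparities and better targeting of areas, not high ratings from participants. The slides (Appendix B) and items (Appendix C) are not in the text. This stands: the strength of the cue is unknown.
- **A reader might infer that the aspirations are the last thing heard and the neighborhood ratings the next thing asked.** The text supports neither. The question period could come after, no item order is given, and the description of the post survey mentions knowledge questions first. This stands: the segment is only the last one listed.
- **Purpose is disclosed before the pre-survey too.** Attendees are told the scope of the study (4.4 A), the consent read aloud covers purpose (10.0), and partner sites hear that the project aims in part "to assess their interest in community health". This stands in part. What is said before both surveys is present at both, so only what the closing segment adds can enter the change. That addition may be small, but it is not shown to be nil.
- **Explaining what a neighborhood approach could yield may be the active ingredient for expectancies.** This is fair for the factual overview, which is why it should stay. It is weaker for the project's own hopes, although the documents draw no line between the two.
- **Changing the order now has costs.** This is Amendment 8 of a small pilot, and a change creates two versions of the session. This stands and limits what the fix should attempt.

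**Conclusion.** The point holds in a limited form. As described, a statement of the project's aspirations comes between the two surveys, and nothing in the plan separates agreement prompted by it from an education effect on interest and outcome expectancies. This is an inference from the design; the documents neither state nor measure such an effect.

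The size cannot be estimated, for the reasons given above. A reader might conclude that the false-positive rate for these outcomes is 11-51%. That is not supported: those figures follow only from an assumed 0.1-0.2 SD shift, zero true effect and paired data. Nor do the documents support extending the concern to the education results as a whole, because knowledge is little touched. The reordering is a cheap improvement and does not call the study into question.

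**What to change.** For sessions still to be delivered:

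- In section 4.3 B and Appendix B, move only the statement of the project's aspirations or hoped-for findings to a short debrief after the post-test. Keep the factual neighborhood-health overview in the module.
- Leave that statement out of any handout, email or text sent before the post-test.
- Record which order each participant received. Keep the pooled analysis as the main one, and describe interest and expectancies by order without subgroup testing, since a sample of 50 to 100 cannot support it.

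The cost is a minor IRB modification and revised slides, handouts and fidelity checklist, including Spanish versions where they exist. No extra visits or staff are needed. The main downside is two session orders within one small sample. Sessions already delivered cannot be changed, and disclosure at consent remains, so the change reduces the ambiguity without removing it.

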## 4.4 Study Procedures

**A. Recruitment and Informed Consent.** The Office of Community Outreach (OCO) has a history of working with multiple community organizations, offering free bilingual education via our community speakers bureau. During our education sessions, community partners coordinate logistics, promote our programs and invite community members to participate. Recruitment of study participants will occur working through these long-standing community partners. Partner sites will promote the study and invite participants to a session to learn more. A recruitment flyer may be used at some sites to advertise the study.

Recruitment efforts will be concentrated in census tracts with the greatest need for intervention, i.e., census tracts identified as high-risk due to socioeconomic factors linked to liver cancer (e.g., % non-Hispanic Black, household stability) and high rates of liver cancer. If no current partners are located in these high-risk census tracts, potential new partners will be identified by searching for community centers, federally qualified health centers, etc.

Individuals who attend the session will be informed about the scope of the study and invited to formally participate by the study team. Individuals interested in participating will be consented by health educator [name], project manager [name], or Co-PI [name] prior to completing the pre-intervention survey. Persons not interested will be thanked for their time and excused. We anticipate recruiting between 50-100 participants, depending on the number of participating community partners and the number of education session completed. Education sessions may be conducted on a one-on-one basis or in a group, depending on the number of interested individuals present at any given session. Individuals who refuse to participate or who withdraw from the project will be treated without prejudice.

Due to the COVID-19 pandemic, in-person recruitment efforts conducted by OCO has ceased. During pandemic-related closures, all study-related activities will be conducted over the phone, online, and through US mail. Recruitment will be conducted over the telephone, and informed consent will be obtained verbally (also over the telephone). Once informed consent is obtained, an oral consent document will be sent via US mail to the participant.

#### **B. Study Survey**

Once eligibility has been confirmed, informed consent has been obtained, participants will fill out a sign-in sheet that includes their street address. If the participant agrees to be contacted about this or future research after their participation, they will also be asked to write their telephone number on this form. Because the sign-in sheet contains identifiable information, it will be kept separate from survey data and will be linked by a study ID assigned to the participant after consent. The street address data will be geocoded for neighborhood analysis. Telephone numbers will be stored in a secure database. Once geocodes are created from the street addresses, hard copies of the sign-in sheets will be destroyed. After the sign-in sheet is collected, the study survey will be administered. Once approved, the English survey will be translated into Spanish language. Once translated, a modification will be submitted.

The study "pre" survey will be administered post informed consent process and prior to the educational intervention by OCO health educators (field staff). Upon completion of the educational module, a posttest survey will be administered. All survey data will be entered in the RedCap database.

Both the pre- and post-survey will contain measures of knowledge about liver risks and prevention, self-efficacy about talking to medical professionals about neighborhood risk, as well as demographic items (e.g. gender, race/ethnicity). The post survey will include similar knowledge questions as well as additional questions specifically related to neighborhood health, including a program evaluation, outcome expectancies about learning about neighborhood health (i.e., the extent to which leaning about neighborhood health will be beneficial), and intentions to talk with clinicians about liver cancer, neighborhood health and liver cancer screening. **Primary outcomes** include pre-post changes in knowledge about liver cancer, interest in learning about neighborhood health, outcome expectancies for learning about neighborhood health, and participant intentions for talking to their doctors about liver cancer risk.

During COVID-19 closures, the survey will be administered over the telephone. Mailing and street address will be collected during recruitment, so that informed consent copies and intervention materials can be mailed to the participant.

# C. Follow-up of Participants

At this juncture, we do not anticipate active follow-up of participants. However, we will include an option on the consent form for patients to be re-contacted should we determine it necessary or if we have other research opportunities.

#### 5.0 Data Management

All study data released to Fox Chase Cancer Center (FCCC) will be kept in a study-specific. secure, password protected, REDCap database (which will be created by the FCCC Population Studies Facility or study team). REDCap (Research Electronic Data Capture; developed by Vanderbilt University in collaboration from a consortium of institutional partners) will be used for electronic data collection and study data management[15]. The REDCap system is a secure, web-based application that is flexible enough to be used for a wide variety of research studies. It offers intuitive interfaces for data entry and real time data validation. REDCap relies on a studyspecific data dictionary that will be defined by the research team. REDCap supports easy data manipulation with audit trails and reporting capabilities, including automated export to common statistical packages (SPSS, SAS, Stata, R). REDCap was developed around HIPAA-Security guidelines, and all web-based information transmissions are encrypted. REDCap currently supports 500+ academic/non-profit consortium partners on six continents and over 70,000 research end-users (www.project-redcap.org). All data will be stored on a server maintained by the FCCC Information Systems and Technology Department in a secure data center. The server is backed up to tape on a daily basis and is protected from inappropriate outside access by commercial grade firewalls.

Separate secure databases will be used to a) store information which could identify participants (e.g., name, local address, contact information, etc) and b) store geocoded de-identified data from regional/state/national data resources for subsequent data linkage. Select research staff will be given access to the study REDCap database. Only research staff involved in patient recruitment/geocoding will have access to information which could identify participants. Only geocoded de-identified data will be used/released for analysis. Address information will be destroyed once geocoding is complete. All data will be destroyed seven years after study closure.

